## **Appendix B: Specification of Data Elements**

See accompanying Excel file “VISIONDataElementsCodebook.”

## Appendix C: Assessment of inclusion criteria

Retrospective cohorts for this protocol will be defined based on care-seeking behavior; however, deriving a cohort based on seeking care could introduce bias to estimates of incidence of influenza-associated outcomes and the effect influenza vaccination on reducing the incidence of such outcomes. To assess the validity and biases associated with the definition of the cohort, the first primary objective of the protocol will assess and compare the demographics, frequency of health-care utilization, and frequency of influenza-related outcomes between cohorts defined in different ways.

Following the protocol, five different inclusion criteria are being considered for defining retrospective cohorts for each influenza season. For the 2017/18 influenza season, or another season as agreed upon by the collaborating sites, each collaborating site will define a retrospective cohort using the definitions outlined in the [Participant Eligibility](#) section. **Of note:** only collaborating sites who have access to and can define a source population based on individual membership in a health system will describe characteristics of a cohort as defined using active participant membership.

The following table is an example of what will be filled out to describe the aggregate characteristics of the defined cohort. Of note, the influenza season is defined from September 1 through May 31 of the following year.

|  | In 12 months prior to start of influenza season, individuals who had: |   |                              |  |                                |
|--|--|---|------------------------------|--|--------------------------------|
|  | ≥1 care encounter a or ≥1 inpatient admission                     | ≥1 ambulatory care encounter b or ≥1 inpatient admission | ≥1 ambulatory care encounter | ≥1 general practice encounter c | Active membership d |
| Number of unique patients in the cohort |  |   |                              |  |                                |
| Demographics                            |  |   |                              |  |                                |
| Age, in years (n, %)                           |  |   |                              |  |                                |
| <2   |  |   |                              |  |                                |
| 2–4  |  |   |                              |  |                                |
| 5–17   |  |   |                              |  |                                |
| 18–49  |  |   |                              |  |                                |
| 50–64  |  |   |                              |  |                                |
| 65–74  |  |   |                              |  |                                |
| 75–84  |  |   |                              |  |                                |
| ≥85  |  |   |                              |  |                                |
| Sex (n, %)                                     |  |   |                              |  |                                |
| Male   |  |   |                              |  |                                |
| Female   |  |   |                              |  |                                |
| Other  |  |   |                              |  |                                |
| Race (n, %)                                    |  |   |                              |  |                                |
| White  |  |   |                              |  |                                |
| Black  |  |   |                              |  |                                |
| Other  |  |   |                              |  |                                |
| Hispanic (n, %)                                |  |   |                              |  |                                |
|  |  |   |                              |  |                                |

| Healthcare utilization  |  |  |  |  |  |
|--|--|--|--|--|--|
| In 12 months before start of influenza season              |  |  |  |  |  |
| General practice office visits, median (IQR) e                |  |  |  |  |  |
| Medical specialty office visits, median (IQR)                            |  |  |  |  |  |
| Urgent care visits   |  |  |  |  |  |
| Emergency department visits, median (IQR)                                |  |  |  |  |  |
| Inpatient admissions, median (IQR)                                       |  |  |  |  |  |
| During influenza season                                    |  |  |  |  |  |
| General practice office visits, median (IQR)                             |  |  |  |  |  |
| Medical specialty office visits, median (IQR)                            |  |  |  |  |  |
| Urgent care visits   |  |  |  |  |  |
| Emergency department visits, median (IQR)                                |  |  |  |  |  |
| Inpatient admissions, median (IQR)                                       |  |  |  |  |  |
|  |  |  |  |  |  |
| Influenza-related outcomes during the influenza season            |  |  |  |  |  |
| Frequency of respiratory-associated hospitalizations (n, %) f |  |  |  |  |  |

a Care encounters include telephone-based care visits, an office-based ambulatory encounter, an urgent care encounter, or an emergency department encounter with the health system.

b Ambulatory care encounters include office-based visits to a general practice office (including but not limited to general pediatrics, general internal medicine, obstetrics/gynecology, or general family medicine), or office-based visits to a medical specialty office (including but not limited to cardiology clinic, diabetes clinic, rehabilitation clinic, gastrointestinal specialist, etc.).

c General practice encounters include office-based visits to a general practice office (including but not limited to general pediatrics, general internal medicine, obstetrics/gynecology, or general family medicine).

d Only applicable to “closed” health systems where individuals enroll as members and enrollment is tracked.

e Median number of visits per individual, with interquartile range (25th–75th percentiles).

f Respiratory-associated hospitalizations should include any qualifying admissions to an inpatient ward for at least 24 hours, or admissions where the discharge date is at least one calendar day after the admission date, if time in hours is not available. Qualifying respiratory admissions include those with a discharge code, in any positions, of 460-519 (for ICD-9 codes) or J00-J99 (for ICD-10 codes).

## Appendix D: Diagnosis Codes and Other Variables Used to Define for High Risk Conditions, ARI Hospitalizations, and Study Outcome

This appendix includes example conditions and codes used to define high-risk conditions and outcomes. These codes may be modified to include additional conditions or diagnoses as objectives are refined. This list of codes can also be found in the data dictionary referenced in Appendix B.

### High Risk Conditions

| Description   | ICD-9 Code   | ICD-10 Code  |
|---|--|--|
| Blood disorders   | 282.*, 283.*, 284*   | D55.*, D56.0, D56.1, D56.2, D56.4, D56.5, D56.9, D57.0, D57.1, D57.2, D57.4, D57.8, D58.*, D59.*, D60.*, D61.*, D64.0, D64.1, D64.2, D64.3, D64.4, D64.8, D65.*, D66.*, D67.*, D68.*   |
| Cerebrovascular disease                                       | 430, 431.*, 432.*, 433.*, 434.*, 435, 436, 437.*, 438.*, 348   | I60.*, I61.*, I62.*, I63.*, I68.*, I69.*   |
| Chronic lung disease  | 031.0*, 135.*, 277.0*, 273.4, 277.6*, 494.*, 495.*, 500.*, 501.*, 502.*, 503.*, 504.*, 505.*, 506.*, 508.*, 510, 513, 514.*, 515.*, 516.*, 517.*, 518.1*, 518.2*, 518.3*, 518.6*, 518.83, 519.9*, 519.0*, 748.4*, 748.5*, 748.6*, 759.3*, 770.2*, 770.7*, V42.6*, 714.81, 769, 770 | D86.0, E84.*, E88.01, J47.*, J60.*, J61.*, J62.*, J63.*, J64.*, J65.*, J66.*, J67.*, J68.*, J69.*, J70.*, J81.*, J82.*, J84.*, J95.0, J96.*, J98.1, J99.*, P25.*, P26.*, P27.*, P28.*, Q33.*, T86.3, T86.8, Z94.2  |
| Chronic lung disease (asthma)                                 | 493.*  | J45.*  |
| Chronic lung diseases (chronic obstructive pulmonary disease) | 491.*, 492.*, 496.*  | J40.*, J41.*, J42.*, J43.*, J44.*  |
| Chronic lung disease (endemic mycoses)                        | 115.*, 116, 116.1, 484.6, 117.3, 518.6, 117.5, 321, 117.7  | B39.*, B40.*, B41.*, B44.*, B45.*, B46.0   |
| Chronic lung disease (pulmonary tuberculosis)                 | 011.*, 012.*   | A15.*, A31.0   |
| Heart disease   | 393.*, 394.*, 395.*, 396.*, 397.*, 398.*, 402.*, 404.*, 415, 416.*, 417.*, 423.*, 424.*, 425.*, 426.*, 427.1*, 427.2*, 427.3*, 427.4*, 427.5*, 427.6*, 427.8*, 429.*, 440.*, 446.*, V42.1*, V45.0*, V45.81, V45.82, 9971, 441.*, 442.*, 443.*, 444.*, 447.*, 4461                  | I01.*, I02.*, I05.*, I06.*, I07.*, I08.*, I09.*, I11.*, I13.*, I26.*, I27.*, I28.*, I31.*, I34.*, I35.*, I36.*, I37.*, I41.*, I42.*, I43.*, I44.*, I46.*, I48.*, I51.*, I52.*, I97.0, I97.1, M31.*, Z94.1, Z95.*, Z98.61, I71.*, I72.*, I73.*, I74.*, I75.*, I79.* |
| Heart disease (congenital heart disease)                      | 745.*, 746.*, 747.*, 759.3   | Q20.*, Q21.*, Q22.*, Q23.*, Q24.*, Q25.*, Q26.*, Q27.0, Q27.3, Q27.4, Q27.8, Q27.9, Q28.*, Q89.3   |
| Heart disease (heart failure)                                 | 428.*  | I50.*  |

| Description                     | ICD-9 Code  | ICD-10 Code  |
|--|--|---|
| Heart disease (ischemic heart disease) | 410.*, 411.*, 412.*, 414.*   | I21.*, I22.*, I23.*, I24.*, I25.*   |
| Immunosuppression                      | 042.*, 43, 44, 136.3*, 279.*, 288.0*, 288.1*, 288.2*, 288.4*, 446.*, 710.0*, 710.1*, 710.2*, 710.3*, 710.4*, 714.*, V08.*, V42.2*, V42.7*, V42.8*, V42.9*, V42.1*, V42.6*, V42.0*, V424, V58.0*, V58.1*, 996.8, 710, 963.1   | B20.*, B59.*, B97.3, D47.Z1, D70.*, D71.*, D72.*, D73.*, D76.*, D80.*, D81.*, D82.*, D83.*, D84.*, D89.*, M05.*, M06.*, M07.*, M08.*, M30.*, M31.*, M32.*, M33.*, M34.*, M35.0, M35.9, Q89.0, Z21*, Z48.2, Z51.0, Z51.1, Z94.*, Z79.5, Z79.82   |
| Immunosuppression (malignancy)         | 140.*, 141.*, 142.*, 143.*, 144.*, 145.*, 146.*, 147.*, 148.*, 149.*, 150.*, 151.*, 152.*, 153.*, 154.*, 155.*, 156.*, 157.*, 158.*, 159.*, 160.*, 161.*, 162.*, 163.*, 164.*, 165.*, 166.*, 167.*, 168.*, 169.*, 170.*, 171.*, 172.*, 174.*, 175.*, 176.*, 177.*, 178.*, 179.*, 180.*, 181.*, 182.*, 183.*, 184.*, 185.*, 186.*, 187.*, 188.*, 189.*, 190.*, 191.*, 192.*, 193.*, 194.*, 195.*, 196.*, 197.*, 198.*, 199.*, 200.*, 201.*, 202.*, 203.*, 204.*, 205.*, 206.*, 207.*, 208.* | C00.*, C01.*, C02.*, C03.*, C04.*, C05.*, C06.*, C07.*, C08.*, C09.*, C10.*, C11.*, C12.*, C13.*, C14.*, C15.*, C16.*, C17.*, C18.*, C19.*, C20.*, C21.*, C22.*, C23.*, C24.*, C25.*, C26.*, C30.*, C31.*, C32.*, C33.*, C34.*, C37.*, C38.*, C39.*, C40.*, C41.*, C43.*, C44.*, C45.*, C46.*, C47.*, C48.*, C49.*, C4A.*, C50.*, C51.*, C52.*, C53.*, C54.*, C55.*, C56.*, C57.*, C58.*, C60.*, C61.*, C62.*, C63.*, C64.*, C65.*, C66.*, C67.*, C68.*, C69.*, C70.*, C71.*, C72.*, C73.*, C74.*, C75.*, C76.*, C77.*, C78.*, C79.*, C7A.*, C7B.*, C80.*, C81.*, C82.*, C83.*, C84.*, C85.*, C86.*, C88.*, C90.*, C91.*, C92.*, C93.*, C94.*, C95.*, C96.*, D03.*, D46.* |
| Liver disease                          | 571.*, 572.1*, 572.2*, 572.3*, 572.4*, 572.5*, 572.6*, 572.7*, 572.8*  | B18.*, I81.*, I85.*, K70.*, K71.*, K72.*, K73.*, K74.*, K75.*, K76.*, K77.*   |
| Metabolic disease                      | 255.*, 270.*, 271.*, 272.*, 277.*, 278.00, 278.01  | E00.*, E01.*, E03.*, E05.*, E06.*, E15.*, E16.*, E20.*, E21.*, E22.*, E23.*, E24.*, E25.*, E26.*, E27.*, E28.*, E29.*, E31.*, E32.*, E34.*, E66.01, E66.2, Z68.4, E70.*, E71.*, E72.*, E74.*, E75.2, E76.*, E77.*, E78.*, E79.*, E80.*, E83.*, E85.*, E88.*   |
| Metabolic disease (diabetes mellitus)  | 250*, 251.* 357.2*, 362.0*, 362.11, 366.41   | E08.*, E10.*, E11.*, E13.*  |

| Description                            | ICD-9 Code   | ICD-10 Code   |
|--|--|---|
| Neurological/Musculoskeletal disorders | 290.*, 294.1*, 318.1*, 318.2*, 330.*, 331.*, 332.*, 333.0*, 333.4*, 333.5*, 333.6*, 333.7*, 333.8*, 333.9*, 334.*, 335.*, 336.*, 340.*, 341.*, 342.*, 343.*, 345, 344.0*, 358.0*, 358.1*, 359.*, 756.1*, 756.3*, 756.4*, 756.5*, 756.6*, 768.5*, 780.3, 780.72 | H49.81, M12.0, M36.0, E75.02, E75.19, E75.4, F01.*, F02.*, F03.*, F71.*, F72.*, F73.*, F84.2, G10.*, G11.*, G12.*, G13.*, G14.*, G20.*, G21.*, G23.*, G24.*, G25.*, G26.*, G30.*, G31.*, G32.*, G35.*, G36.*, G37.*, G40.*, G45.*, G46.*, G60.*, G61.*, G62.*, G63.*, G64.*, G70.*, G71.*, G73.*, G80.*, G81.*, G82.*, G83.*, G90.3, G91.*, G93.*, G94.*, G95.*, G99.2, P91.*, Q00.*, Q01.*, Q02.*, Q03.*, Q04.*, Q05.*, Q06.*, Q07.*, Q76.*, Q77.*, Q78.*, Q79.*, Q85.*, Q87.4, Q90.*, Q91.*, Q92.*, Q93.*, Q96.*, R41.*, R53.2, R54.* |
| Renal disease                          | 285.21, 403.*, 581.*, 582.*, 583.*, 585.*, 587.*, 588.0*, 588.1*, 590.0* 593.8, V42.0*, V56.*, V45.1*  | I12.*, N01.*, N02.*, N03.*, N04.*, N05.*, N06.*, N07.*, N08.*, N11.*, N14.*, N15.*, N16.*, N18.*, N25.*, N26.*, N28.*, Q27.1, Q27.2, Q60.*, Z49.*, Z91.15, Z94.0, Z99.2   |

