### ***High risk conditions***

For the primary objectives, high risk conditions will be defined using ICD diagnosis codes. A patient with at least 1 inpatient encounter or at least 1 outpatient encounter with a high-risk ICD diagnosis code (see Appendix D) recorded in the 12 months prior to the current influenza season will be considered as having a high-risk condition. The following high-risk conditions will be defined:

- Chronic lung disease;
  - Asthma;
  - COPD;
  - Pulmonary tuberculosis
  - Endemic mycoses

- Chronic metabolic disease;
  - Diabetes mellitus;
- Blood disorders;
- Cardiovascular disease;
  - Coronary artery disease;
  - Heart failure;
  - Congenital heart disease;
- Neuromuscular disorder;
- Neurologic disorder;
- Immunocompromised condition;
  - Solid organ malignancy;
  - Hematologic malignancy;
  - Solid organ transplant;
  - Hematopoietic stem cell transplant;
- Chronic renal disease;
- Gastrointestinal/liver disease;
- Rheumatologic/Autoimmune condition.

Additional underlying conditions, including, but not limited to, pregnancy, sickle cell disease, hypertension, obesity, and cystic fibrosis have also been associated with increased risk of severe influenza or COVID-19 disease and thus might be further defined and explored in the network.

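### Appendix D's paired ICD-9 and ICD-10 lists do not define the same high-risk strata, so several strata change content between ICD-9 and ICD-10 seasons

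*Protocol*

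**What the plan says.** The rule for entering a stratum is in protocol section 5.4, under high risk conditions: "A patient with at least 1 inpatient encounter or at least 1 outpatient encounter with a high-risk ICD diagnosis code" qualifies, and the code must be a "high-risk ICD diagnosis code (see Appendix D) recorded in the 12 months prior to the current influenza season". One coded encounter is enough, and Appendix D supplies the codes.

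Section 5.1 allows seasons from 2010/11 to 2018/19, with each site choosing its own. Appendix D prints an ICD-9 and an ICD-10 list for each condition, with no crosswalk. Examples of the paired cells:

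- Immunosuppression, end of the ICD-10 list: "M35.0, M35.9, Q89.0, Z21*, Z48.2, Z51.0, Z51.1, Z94.*, Z79.5, Z79.82". From the V58 family the ICD-9 cell has only V58.0 and V58.1.
- Malignancy, ICD-9: "170.*, 171.*, 172.*, 174.*, 175". ICD-10: "C41.*, C43.*, C44.*, C45".
- Metabolic disease, ICD-9: "255.*, 270.*, 271.*, 272.*, 277.*, 278.00, 278.01". The ICD-10 cell opens "E00.*, E01.*, E03.*, E05.*, E06".
- Chronic lung disease, ICD-10: "J95.0, J96.*, J98.1". The only respiratory-failure code in the ICD-9 cell is 518.83.

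Section 4.1 makes incidence (objective 4) and VE (objective 5) by high-risk condition primary objectives. Section 6.1 also lists high-risk conditions among the possible confounders in the VE models.

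**The concern.** When a stratum is defined by one code, its membership is whatever the list says. If the two columns of a row do not cover the same conditions, people with the same health state are in the stratum in one coding era and outside it in the other. A difference in incidence or VE between an ICD-9 season and an ICD-10 season could then reflect the list and not influenza or the vaccine.

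A second problem lies within the ICD-10 era. If a listed code does not denote the named condition, the stratum mixes the people of interest with others. Section 3.2 names VE among people with underlying conditions as a main reason for building the network, so this contrast should not be blurred by the definition.

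Sites choose their seasons, so the share of ICD-9 and ICD-10 seasons can differ between sites. If a site's estimate combines its seasons, the planned look at heterogeneity of VE across sites could confuse coding era with site.

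**Working it through.** **Inputs.** The presence or absence of each code was read from Appendix D. The high-risk table prints no code labels, so code meanings come from the public ICD classification. The protocol gives no date for the coding switch and no prevalence for any code. It states no figure on this point, so there is none to reproduce.

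**Step 1: rows side by side.**

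| Row | ICD-9 cell | ICD-10 cell | ICD-10 against ICD-9 |
|---|---|---|---|
| Immunosuppression | V58.0 and V58.1 (partners of Z51.0 and Z51.1); no long-term drug-use code | adds Z79.5 (long-term steroids) and Z79.82 (long-term aspirin) | broader |
| Malignancy | 140 to 208 with one gap, 173 (non-melanoma skin cancer) | includes C44 (the same disease) | broader |
| Metabolic, thyroid | none | E00, E01, E03, E05, E06 | broader |
| Metabolic, obesity | 278.00 (unspecified) and 278.01 | E66.01, E66.2 and Z68.4 only | narrower |
| Chronic lung | 518.83 (chronic respiratory failure) | all of J96, so acute failure too | broader |
| Blood | 282 to 284 | adds D65 to D68 (coagulation); no 286 in ICD-9 | broader |
| Cerebrovascular | includes 433, 434 and 437 | no I65 to I67 | narrower |
| Heart | includes 440 | no I70 | narrower |
| Diabetes | includes 251 | no counterpart in the row; E15 and E16 are under Metabolic | narrower |

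The shifts run in both directions and sit in different rows. Lipid disorders (272 and E78) are in both columns, so they raise a question of breadth but not of the switch.

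**Step 2: would a planned check find this?** The internal crosschecks in section 7.4 compare extracted proportions with the source data. Both carry the same codes, so they would agree. The external comparisons in that section are across sites and with national, regional or state data, not across the switch. The minimum chart-review elements in Appendix G are vaccination, testing, death, ICU admission and ventilation; high-risk conditions are not among them.

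**Step 3: possible dilution of the Immunosuppression row in ICD-10 seasons.** All values here are assumed. Let p be the prevalence of true immunosuppression and a the prevalence of an added code that does not denote it, taken as independent. The wrongly included share is

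f = a(1 − p) / [p + a(1 − p)].

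- p = 10%, a = 0.5%: f = 0.0045 / 0.1045 = 4%.
- p = 3%, a = 5%: f = 0.0485 / 0.0785 = 62%.
- p = 2%, a = 20%: f = 0.196 / 0.216 = 91%.
- At p = 3%, f is 24%, 49%, 62% and 76% for a = 1%, 3%, 5% and 10%.

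The added people become the majority once a(1 − p) exceeds p.

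**Step 4: effect on the estimates.** Assume VE of 20% in the truly immunosuppressed and 40% in those wrongly included, and let r be the ratio of their unvaccinated risks. Then

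stratum VE = 1 − [(1 − f)·r·0.8 + f·0.6] / [(1 − f)·r + f].

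At p = 3% and a = 5% (f = 0.618):

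- r = 1: 1 − 0.676/1.000 = 32.4%.
- r = 2: 1 − 0.982/1.382 = 28.9%.
- r = 4: 1 − 1.593/2.146 = 25.8%.

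The denominators are also the stratum's unvaccinated risk relative to the wrongly included people: 1.38 where the true ratio is 2, and 2.15 where it is 4. The direction follows whenever the added people are not immunosuppressed and differ in risk or VE. The size depends wholly on the assumed values.

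**The case against.** The strongest reply is that Appendix D is not final. It calls its codes examples that may be modified and points to a data dictionary that is not at hand, and section 7.1 says operational definitions will be agreed collaboratively. This tempers the point but does not remove it. Section 5.4 defines high risk by Appendix D, the appendix says the same list is in the dictionary, and the only change it foresees is adding conditions or diagnoses.

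A second reply is that partial safeguards exist. Section 7.4 suggests that sites could cross-check conditions against medication use, and section 4.2 lists refinement of conditions by medication and laboratory data. The first is optional and the second is a secondary objective that depends on resources. Neither compares coding eras.

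Third, within one season vaccinated and unvaccinated people are classified by the same list, so the switch does not by itself bias that season's VE. This stands. The harm from the switch is to comparison or combination across seasons; the aspirin code separately changes whose VE is estimated in ICD-10 seasons.

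Stronger readings are tempting but not supported:

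- A reader might infer that the immunosuppressed stratum is largely made up of wrongly included people. With no prevalences given, that is unproven.
- A reader might infer that the mismatches add up in one stratum. They sit in different rows; skin cancer, thyroid and respiratory-failure codes do not dilute the general Immunosuppression row.
- A reader might infer that the plan pools seasons. Section 6.1 speaks of pooling across sites, and cohorts and incidence are defined season by season.

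**Conclusion.** The point holds as a defect of definition. The paired lists are not equivalent in at least eight rows, and under the one-code rule those strata change content between ICD-9 and ICD-10 seasons, some widening and some narrowing. Stratum-specific incidence and VE are therefore not comparable across the switch, and no planned check is aimed at detecting this. The conclusion needs no assumed prevalence; it rests on the printed codes and their standard ICD meanings.

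The immunosuppressed stratum may in addition be substantially diluted in ICD-10 seasons. The size cannot be fixed from the documents: the assumed share runs from 4% to 91%, and the VE figures above are illustrations only. The lists should be corrected before the strata are derived; the overall design is not in question.

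**What to change.** Map the two columns of Appendix D code by code and make each row equivalent.

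- Immunosuppression: remove Z79.82. Either drop Z79.5, or limit it and add an ICD-9 long-term steroid counterpart, noting any remaining difference in specificity. Restricting Z79.5 alone is not enough, because steroid users would still enter only in ICD-10 seasons. Check the remaining codes in the row in the same pass.
- Malignancy: treat 173 and C44 alike, both in or both out.
- Metabolic: treat thyroid disease alike in both eras and use one obesity threshold.
- Chronic lung: align 518.83 and J96.
- Blood, Cerebrovascular, Heart and Diabetes: reconcile D65 to D68, I65 to I67, I70 and 251 with the opposite column.

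Before seasons are compared or combined, report each stratum's prevalence by season and site across the switch, and explain any step.

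The cost is a revision of the appendix and codebook and a re-run of the derivation at the sites or the coordinating center. Some strata become smaller, which reduces precision in the less common conditions.

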## Respiratory Outpatient Visits and Hospitalizations

Respiratory outpatient visits and hospitalizations will be defined using the following ICD-9 and ICD-10 diagnosis codes. Codes can be in any position. For hospitalizations, only discharge codes should be considered. Encounters occurring in the outpatient clinic, emergency department, urgent care, or via telehealth should additionally include encounters with codes related to signs/symptoms (at the bottom of the table).

| Description   | ICD-10*
code |
|--|-------------------------|
| Pulmonary anthrax  | A22.1*                  |
| Whooping cough   | A37*                    |
| Other specified sepsis   | A41.89                  |
| Legionnaire's Disease  | A48.1*                  |
| Cytomegaloviral pneumonitis  | B25.0*                  |
| Viral infection of unspecified site  | B34 *                   |
| Aspergillosis  | B44 *                   |
| Adenovirus   | B97.0*                  |
| Enterovirus  | B97.1*                  |
| Coronavirus  | B97.2*                  |
| Respiratory syncytial virus as the cause of diseases classified elsewhere                | B97.4*                  |
| Other viral agents as the cause of diseases classified elsewhere                         | B97.8*                  |
| Acute suppurative otitis media   | H66.0*                  |
| Suppurative otitis media, unspecified  | H66.4*                  |
| Otitis media, unspecified  | H66.9*                  |
| Otitis media in diseases classified elsewhere  | H67 *                   |
| Diseases of the respiratory system   | J00-J99 *               |
| Other viral diseases complicating pregnancy, childbirth and the puerperium               | O98.5*                  |
| Diseases of the respiratory system complicating pregnancy, childbirth and the puerperium | O99.5*                  |
| COVID-19   | U00                     |
| COVID-19   | U07.1                   |
| COVID-19   | U49                     |
| Encounter for observation for suspected exposure to biological agents ruled out          | Z03.81 *                |
| Encounter for observation for other suspected diseases and conditions ruled out          | Z03.89 *                |
| Encounter for screening for respiratory tuberculosis                                     | Z11.1 *                 |
| Encounter for screening for other bacterial diseases                                     | Z11.2 *                 |
| Encounter for screening for other viral diseases   | Z11.5 *                 |
| Encounter for screening for other viral diseases   | Z11.59 *                |
| Encounter for screening for other infectious and parasitic diseases                      | Z11.8 *                 |

|  |           |
|--|-----------|
| Encounter for screening for infectious and parasitic diseases, unspecified   | Z11.9 *   |
| Contact with and (suspected) exposure to other viral communicable diseases   | Z20.82 *  |
| Contact with and (suspected) exposure to other viral communicable diseases   | Z20.828 * |
| Contact with and (suspected) exposure to other communicable diseases   | Z20.89 *  |
| Contact with and (suspected) exposure to unspecified communicable disease  | Z20.9 *   |
| Mucocutaneous lymph node syndrome [Kawasaki]   | M30.3 *   |
| Encounters occurring in the outpatient clinic, telehealth, emergency department, or urgent care should additionally capture encounters with these codes           |           |
| Hemorrhage from respiratory passages, cough, abnormalities of breathing, pain in throat and chest, other symptoms/signs involving the circulatory and respiratory system | R04-R09 * |
| Fever  | R50 *     |
| Headache   | R51 *     |
| Malaise and fatigue  | R53 *     |
| Shock, unspecified   | R57.9 *   |
| Symptoms and signs specifically associated with systemic inflammation and infection  | R65 *     |
| Chills without fever   | R68.83 *  |

[figure not shown]
\*For the complete list these of codes, please refer to the data dictionary referenced in Appendix B.

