***Objective 5: Assessment of vaccine effectiveness***

- We will estimate the effect of influenza vaccination on risk of lab-confirmed influenza-associated respiratory hospitalization by age group, influenza type/subtype, and high-risk conditions
  - The risk of influenza-associated respiratory hospitalization among cohort members who were or were not vaccinated with the current season influenza will be compared using appropriate methods for longitudinal data with time varying exposure, including Poisson regression or proportional hazards modeling.
  - VE will be estimated as  $(1 - \text{adjusted relative risk}) \times 100$ .
  - We will assess and adjust for confounders as appropriate. These may include characteristics such as age, sex, site, race/ethnicity, high-risk health conditions, prior healthcare utilization, time of event during the influenza season, etc.
  - Data collected for this study are intended to be pooled across sites. VE will first be estimated for each site and heterogeneity in estimated VE across sites examined.
- We will estimate the effect of influenza vaccination on risk of lab-confirmed influenza-associated ARI outpatient visit among children (adults only if influenza testing allows for this) by age group, influenza type/subtype, and high-risk conditions
  - The risk of influenza-associated outpatient visits among cohort members who were or were not vaccinated with the current season influenza will be compared using appropriate methods for longitudinal data with time varying exposure, including Poisson regression or proportional hazards modeling.
  - VE will be estimated as  $(1 - \text{adjusted relative risk}) \times 100$ .

- We will assess and adjust for confounders as appropriate. This may include characteristics such as age group, sex, site, race/ethnicity, high-risk health conditions, prior healthcare utilization, time of event during the influenza season, etc.
- Data collected for this study are intended to be pooled across sites. VE will first be estimated for each site and heterogeneity in estimated VE across sites examined.
- VE analyses against influenza-associated respiratory hospitalizations will also be conducted using a test-negative case-control design
  - This analysis will be conducted among individuals who were hospitalized for acute respiratory illness during the influenza season and who were tested for influenza.
  - Cases will be defined as hospitalized individuals who tested positive for influenza.

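### Appendix D lets a lone screening, exposure or ruled-out code, or any J code in any position, make an encounter respiratory, which misdefines the Objective 3 denominators and the test-negative population

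*Protocol*

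**What the plan says.** Section 5.5 of the protocol defines respiratory hospitalizations and ARI outpatient visits by the codes in Appendix D, and section 7.2 confirms that Appendix D defines ARI hospitalizations. The rule there is: "Respiratory outpatient visits and hospitalizations will be defined using the following ICD-9 and ICD-10 diagnosis codes. Codes can be in any position". The one limit for inpatients is "For hospitalizations, only discharge codes should be considered".

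The list includes, by its own descriptions:
- ruled-out encounters (Z03.81, Z03.89), for example "Encounter for observation for other suspected diseases and conditions ruled out";
- screening encounters (Z11.1, Z11.2, Z11.5, Z11.59, Z11.8, Z11.9), for example "Encounter for screening for respiratory tuberculosis" and "Encounter for screening for other bacterial diseases";
- exposure encounters (Z20.82, Z20.828, Z20.89, Z20.9), for example "Contact with and (suspected) exposure to unspecified communicable disease";
- the whole respiratory chapter, J00-J99.

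All of these rows stand above the divider that introduces the codes reserved for outpatient, telehealth, emergency and urgent care encounters. They therefore define hospitalizations as well.

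In section 6.1, Objective 5, the test-negative analysis is confined to individuals "hospitalized for acute respiratory illness during the influenza season and who were tested for influenza". Controls are those in that group who tested negative. Objective 3 estimates the proportion of respiratory hospitalizations and of ARI visits that were tested, and relates testing to high-risk conditions among other factors.

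**The concern.** The population named in section 6.1 and the population that Appendix D delivers are not the same. An admission that carries only a screening or ruled-out code satisfies Appendix D, although its description says that no illness was established. A test-negative analysis relies on cases and controls coming from the same source, here people admitted with ARI. Controls admitted for other reasons may have different vaccination coverage, and then VE is biased.

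The J00-J99 range raises a separate problem for Objective 3. The high-risk table in the same appendix uses J45 for asthma, J40-J44 for COPD and further J codes for other chronic lung disease. A stay for an unrelated reason enters the denominator if COPD is recorded as a secondary code. The same stay in a patient without COPD does not. The objective is meant to measure bias in clinical testing, and a difference in testing by high-risk status could arise partly from the code list itself.

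**Working it through.** **Text check.** The protocol states no figure on this point, so there is none to reproduce. Sections 5.5 and 7.2 send the definition to Appendix D. Appendix D asks for one listed code in any position. Section 6.1 adds an influenza test, but no acute code, principal-position rule or symptom criterion. Appendix C, footnote f, used for Objective 1, also takes J00-J99 in any position but has no Z codes, so the protocol holds two definitions of a respiratory admission.

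**Overlap of the two lists.** The high-risk lung rows contain 25 J-code entries inside J00-J99: J40-J44 (5), J45 (1), and J47, J60-J70, J81, J82, J84, J95.0, J96, J98.1 and J99 (19).

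**Proportion tested (Objective 3).** Assumed: 50% tested in true ARI stays, 10% tested in other stays, and a share s of other stays in the denominator.

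Measured proportion = (1 - s) x 0.50 + s x 0.10

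| s | Measured proportion tested |
|---|---|
| 0 | 50% |
| 10% | 46% |
| 20% | 42% |
| 30% | 38% |

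If s were 30% in patients with COPD and 0 in patients without, the full 12-point gap would come from the definition, with identical testing of true ARI.

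**Share of non-ARI stays among controls.** A control must have been tested, which filters out most non-ARI stays. With the same assumptions and s = 30%:
- tested ARI stays: 0.70 x 0.50 = 0.35
- tested other stays: 0.30 x 0.10 = 0.03
- share of tested stays that are not ARI: 0.03/0.38 = 7.9%

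If a fifth of tested ARI stays are positive (assumed) and all other stays test negative, ARI controls are 0.35 x 0.8 = 0.28. The non-ARI share of controls is then 0.03/0.31 = 9.7%, or about 10%.

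**Effect on test-negative VE.** Assumed: true VE 40%, 10% of controls non-ARI, and cases unaffected. Coverage in ARI controls is taken as 45.7%, the mean of the adult values in section 6.2: (30 + 42 + 65)/3. Coverage in non-ARI controls differs by d.

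- Case odds = 0.60 x 0.457/0.543 = 0.505
- Control coverage = 0.457 + 0.10 x d
- VE = 1 - case odds/control odds

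| d | Control coverage | Control odds | VE read |
|---|---|---|---|
| -10 points | 0.447 | 0.808 | 37.5% |
| 0 | 0.457 | 0.842 | 40.0% |
| +10 points | 0.467 | 0.876 | 42.4% |
| +15 points | 0.472 | 0.894 | 43.5% |

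These are crude values, before any covariate adjustment.

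**The case against.** **The codes are only examples, and the full list is in a codebook.** Appendix D does call its codes examples and refers to a data dictionary that is not shown. But it foresees modification only to include more conditions or diagnoses, and section 5.5 relies on the list as it stands. This lowers certainty about what sites will apply. It does not cure the stated rule.

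**Adjustment would deal with it.** Section 6.1 names high-risk conditions and prior healthcare utilization as possible confounders in the test-negative model. Adjusting for them addresses part of the coverage difference, so the crude shifts above overstate what would remain. The adjustment is optional in the text, however, and it does not restore the intended population. In Objective 3, adjusting for COPD cannot remove an artifact that COPD status itself creates.

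**Objective 3 already looks at diagnosis codes.** Section 4.1 lists them as a factor in testing, and Appendix A lists discharge diagnosis codes as a stratification variable. Dilution by code group could therefore be seen in the output. That helps interpretation, but the headline proportion still rests on the wrong denominator.

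**Broad capture is useful.** This stands for extraction, and the fix leaves extraction alone.

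**Stronger readings that a reader might infer:**
- *That VE could be off by 8 to 10 points.* That takes about 30% of controls to be non-ARI. At the testing and positivity rates assumed here, about 63% of all respiratory hospitalizations would then have to be non-ARI: 0.1x/(0.1x + 0.4(1 - x)) = 0.30 gives x = 0.63. Nothing in the protocol suggests this.
- *That incidence and cohort VE are diluted too.* Their denominators are cohort person-time and their events require a positive influenza test, so the list adds no denominators or controls there.
- *That J codes on the high-risk list mark stable disease and should not qualify in a secondary position.* The list uses wildcards. In ordinary ICD-10 use J44, J45, J69, J81 and J96 also cover acute episodes. Removing them outright could lose severe influenza stays.

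**Conclusion.** The point holds for two uses of the list: the Objective 3 denominators and the eligibility of test-negative controls. Appendix D admits encounters that its own descriptions mark as screening, exposure or ruled out, including hospitalizations, while section 6.1 names a population with ARI. For J codes, the firm consequence is that high-risk lung disease itself brings stays into the Objective 3 denominator, which can distort the comparison of testing by high-risk status.

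The documents give neither the size nor the direction. On the assumed values, the proportion tested falls from 50% to 38% at a 30% non-ARI share. A true test-negative VE of 40% reads about 38% to 44% before adjustment when about 10% of controls are non-ARI and their coverage is 10 points lower to 15 points higher. With equal coverage there is no bias. The VE effect is therefore modest, and Objective 3 is the more exposed. The test-negative analysis is additional to the cohort analysis of VE, whose person-time denominators are not touched.

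**What to change.** Keep the present Appendix D list for data extraction. For Objective 3 and the test-negative analysis, add one rule: a Z03, Z11 or Z20 code does not qualify an encounter unless another listed respiratory code is present or, for outpatient visits, a listed symptom code. This also brings the list closer to Appendix C, footnote f.

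For chronic J codes in a secondary position, leave the main definition as it is. Add a sensitivity analysis restricted to encounters with an acute respiratory code, using a list settled code by code, because several of the overlapping codes can be acute.

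The cost is one added column in the Appendix D table and the codebook, plus the code-by-code review for the sensitivity analysis. No new data are needed, since diagnosis codes are already extracted (section 5.6). The downside is that a few ARI encounters recorded only under a Z code will be lost.
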